Appendix I

Description of Impedance and Infrared Subsystems of the Mark I

SwissTom Electrical Impedance Tomography (EIT) System:

Name of device: Pioneer Set (Electrical Impedance Tomography System)

Device Manufacturer: SwissTom AG (Parent company SenTec AG)

This device monitors dynamically changing perfusion physiology. To record multiplexed impedance signature from two arrays of 16 electrodes, one array is placed around the thorax above the nipple line and the second array alternates patient to patient between the upper abdomen at the level of the liver-spleen, and the proximal thigh at the femur mid-shaft. The Impedances are recorded between multiple sets of electrodes.

SwissTom developed a clinical EIT system that is approved for pulmonary imaging. This Pioneer system is their research platform that has similar functionality and safety performance to their clinical system but provides research teams with access to raw data and additional functionality for specifying imaging parameters (e.g. control of frame rates, signal frequency acquisition, electrode drive patterns).

Continuous-wave Near-Infrared Spectroscopy (CW-NIRS) Device, custom built:

The device is built on an Ocean Optics FLAME USB Spectrometers, with two OSRAM 4736 NIR LEDs in plastic holders meant to be taped or strapped to the patient on the chest/torso. Probe holders are designed to collect light from surface of skin by means of a mirror and collimator. The device will collect data on light attenuation of muscle in models of shock/trauma. The light output is below the ANSI limits for maximum permissible skin exposure.

ScioSpec MultiChannel Electrical Impedance Spectroscopy (EIS) System:

Name of device: ISX-Mini (MultiChannel Electrical Impedance Spectroscopy System)
Device Manufacturer: ScioSpec

To record multiplexed impedance signatures- arrays of 4 electrodes is placed around the thorax, arm, and thigh of the patient and impedance spectroscopy signatures are recorded. This device monitors dynamically changing intrathoracic and intra-abdominal physiology.

3

Appendix II

Multivariate Systems Inc.™ Mark I Prototype

Setup and Operation Instructions

[figure not shown]
Patient and Wearables Setup

Patient preparation

1. Ensure patient documentation is completed
2. Patient is supine on the table
3. Ensure the device location is suitable to reach all test locations (within 10 feet of cable distance) and is plugged in
4. Shave electrode locations on the patient if there is excessive hair

[figure not shown]
Note: for applying electrodes, it may be more comfortable for the patient to connect the electrode pad to the snap fitting **before affixing to the patient**

5. Apply Electrical Impedance Tomography (EIT) electrodes – two (2) sets of 16 electrodes each. Ensure each ring of electrodes set is installed in the same horizontal plane.

- a. Apply electrodes 1-16 (branches A and B) as per protocol

- b. Apply electrodes 17-32 (branches C and D) as per protocol
- c. To improve even spacing of pads, place electrodes 1, 5, 9, and 13 at the 12, 3, 6, and 9 o'clock positions first, then fill in the three (3) electrodes between them
- 6. Apply Electrical Impedance Spectroscopy (EIS) electrodes as per protocol – three sets of 4 electrodes each

[figure not shown]
- 7. Apply Near Infrared Spectroscopy (NIRS) probes as per protocol – each probe is labeled according to the location on the patient. Place each probe with the cables directed away from the patient's head.
- 8. Apply the dedicated clinical monitor electrode stickers – three probes, white, black and red. The ECG cables can be connected after the electrode pads are placed. Place the plethysmography probe on a patient's finger.

System Configuration and Setup

[figure not shown]
1. Turn the system on
 - a. Ensure the overall system power switch (rear of right side of system enclosure) is turned to the “ON” position.
 - b. Turn switch on the NIRS plate to the on (down) position.
 - c. The monitor may need to be turned on by pressing the power button in rear of the lower right side.
 - d. If power does not start, check that the uninterrupted power supply is on by viewing the power button through the hole in the front of the system.
2. Turn on the dedicated clinical monitor (do NOT interface with the existing clinical monitor) by pressing and holding the power button. ECG and plethysmography data should be displayed upon startup.
3. In the desktop folder, “Data Output,” create a folder for the date and patient number using the following format: Month Day, Year Patient ###. Use the template folder, if desired.

Initialize software packages

3. Clinical monitor: Open the desktop icon “iCollect - shortcut”

[figure not shown]

- a. At the following menu, ensure the settings in the orange box are as shown below and click “Online”

Ga

4. EIS: Open the desktop icon, “EIS - Sciospec Start – Shortcut”

[figure not shown]
a. On the following screen, make sure the “USB” icon is selected, then click “Serial”

[figure not shown]
b. In the subsequent menu, select “COM5.” If COM5 is not an option, it means the EIS device is not found.

- First try restarting the software
- Next try restarting the computer
- If neither of these allow COM5 to be found, check the connections on the ISX-3 mini – requiring removal of the REAR panel of the enclosure.
 - Confirm the white USB cable is fully inserted into the device – the computer should make a sound when the connection is identified
 - Confirm the power cable to the ISX-3 mini is plugged in (small black cable into ISX-3 mini, try unplugging and replugging in the power cable)
 - Cycle the power switch on the back of the ISX-3 mini

[figure not shown]
c. Once you select the COM5 port, the device should appear in the list as shown below

[figure not shown]
- d. Click, “connect”
- e. Once connected, the software will look like this. Click the “load” button, which will open the window to select the setup file (.setUp) to use.

- f. Open the setup file, “Mark-1.setUp” located at the following directory: C:\Users\Mark-1\Desktop\Software\Loaded to PCs\Sciospec ISX3v2_Dartmouth

[figure not shown]
- g. You should now see the setup in the measurement window, called “Mark-1.setUp.” Open this file.
- h. Click on the “setup” under the measurements folder and it will load the frequency settings in the Frequency-Setup display just above it.

[figure not shown]
- i. Click the Autosave option and set the directory to the data output directory you made for this patient: C:\Users\Baystate\Desktop\Data Output\ Month Day, Year Patient ###\EIS
- 5. EIT: Open the desktop icon, “EIT - STEM run - Shortcut”

[figure not shown]
- a. At the bottom left, confirm the software is showing the Sensor Belt Connector as Connected. If the software says the Sensor Belt Connector is disconnected, it indicates an internal power or connectivity problem, requiring the enclosure to be opened. Check if:
 - i. The power cable to the Pioneer Interface Module is fully inserted
 - ii. The cable connector on the front of the Pioneer Interface Module is connected

[figure not shown]
6. NIRS: Open the desktop icon, “NIRS - OceanView”

[figure not shown]
a. Upon initialization the Welcome Screen will look like this. Select Load a Saved Project.

[figure not shown]
b. Select the file, “Mark_1_Oceanview_Project_File.ocv” located at the following directory (if the correct folder does not appear initially): C:\Users\Baystate\Desktop\Software\Loaded to PCs\OceanView 2.0

[figure not shown]
c. Select the Flame-S spectrometer as shown below and click OK

d. Open “Configure graph saving” icon.

- e. **Uncheck** the option to stop after 1 sample.
- f. Configure the destination folder (Target Directory) to the desired Data Output directory and click **Apply**, then **Exit**

- g. **Sensor calibration:** The NIRS probes require some level of calibration data, by connecting the probes to the calibration blocks and collecting data as you would on a patient. This data is not needed regularly if the probes are consistently used on the same body part or do not get damaged. Label calibration data accordingly.

Data Collection

Prior to beginning data collection, quickly ensure all cables have been attached to the patient.

1. Clinical Monitor:

[figure not shown]
- a. Click the save (looks like a floppy disk) icon to start data recording.
- i. A window will pop up asking where to save the file. Navigate to the “Clinical Monitor” folder in the Data Output directory. Name the file “Patient number, date” and click OK. Data is now being recorded and saved.

- b. Click the stop icon to stop and save data at the end of measurements.

2. EIS:

- a. When ready to begin collecting data, click, “measure.” You should see measurements begin in the window below the setup heading.
- i. To view data as it is collected, right click the setup and select, “add new PlotterGrid – ABS/Phase”

[figure not shown]
- ii. There are six plots: two plots per set of electrodes. One plot measures impedance (Z) vs frequency (f), and the other plots phase (Φ) vs frequency. Each plot is labelled at the top, indicating which group of EIS cables it corresponds to (see below table).

Slide Chip	Group Number	Probes Location
1 1 1 1	1	Arm
3 2 3 2	2	Chest
5 3 5 3	3	Leg

- iii. Impedance is measured in Ohms (Ω), phase is measured as an angle ($^{\circ}$), and frequency is measured in Hertz (Hz).
- iv. For the Z vs f plots, right click on the plot area and select, “double-log” view
 - 1. Impedance should be below 1,000 Ω . If the impedance is much higher, it likely means a poor connection at the electrode pad/patient interface
 - a. See the above table to help identify which group has the poor connection
 - b. After checking the electrode pad/patient connections (hair, peeling electrode pad, etc), the next place to check for connectivity problems if impedance is still high is the connection at the system enclosure. Remove and plug in the cable fittings of the problem group.

3. EIT:

[figure not shown]
- a. Click “Apply” to begin data measurements – the computer will not record/save the data until you select the save icon.

[figure not shown]
- i. Once you click “Apply” the other tabs should be selectable to see measurements and electrode connectivity
- ii. Check the “Sensor Quality” tab to check for any connectivity issues with the electrodes or cables

1. The best way to identify problem probes is by looking at the individual impedance values of each electrode
2. Electrode connectivity problems usually occur at the electrode pad/patient connection

- b. On the “Configuration” tab, click the green save icon to begin recording the data – the icon should turn red and the software will indicate data is recording

[figure not shown]

- c. The “Manage Files” icon will bring up a screen allowing you to view and access saved data, ensuring data is being recorded, and later, for copying completed files to the Data Output directory. The “Explore to Data Folder in OS” opens the folder containing the EIT data files.

[figure not shown]

4. **NIRS:**

- a. The probes should sequentially light up. If *not*:
 - i. If one light on the NIRS panel stays illuminated, it is indicating an error with the probe itself or a setting within the software
 1. Before replacing or repairing probes, try cycling the NIRS system power by turning off the Uninterrupted Power Supply
- b. Press the play icon

c. “Start all file writer” (space) to start recording

d. “Pause graph saving” data recording (download icon) to stop

Data Saving and Transmission

NIRS

- a. Should be saving as data is collected. Check the “saved data” tab in Oceanview, or the selected destination folder

EIT

- a. Click the “Manage Files” icon, then “Explore to Data Folder in OS” which will bring you to the folder where the EIT data is stored. Cut/paste the file you just created to the “Data Output Directory”

EIS

- a. Click “measure” again to stop data collection.
- b. Check that the data has been autosaving in the desired directory. If not, click the “save” icon
- c. In the popup window, select, “include sub-data”
- d. Save to the EIS folder in the Data Output directory

Monitor

- a. Select the “Stop saving” icon. Ensure the .drc file for your experiment is located in the Data Output directory

Data Transmission

- a. There are multiple options for transmission of data to outside storage
 - a. A UBS port is available in the rear of the enclosure where an external hard drive can connect. Copy the desired files from the prototype PC to the external drive.
 - b. The PC is configured to be operated remotely (RemotePC software) so long as the PC is connected to the internet and turned on. An external user with the proper credentials can control the PC remotely to configure data transmission.
 - c. The RemotePC software also has a data file transfer function, which can be accessed using the desktop version of the software. This method is not recommended for large data sets as the file transfer capability within the RemotePC software is unreliable for the time duration required to transmit these large files.

Shutdown

1. Switch off the NIRS switch on the faceplate
2. Place the NIRS probes in their holster or somewhere else where they are secure.
3. Close-down software once you have confirmed the data is properly saved in the Data Output directory.
4. Shut down the system by pressing the power button on the Uninterrupted Power Supply, then flipping the switch at the back right of the system enclosure.
5. Disconnect all probes and electrodes from the patient, storing them safely, minimizing any bending tension at the cable/enclosure connections.
6. Disconnect the power chord from the wall and unlock the wheels before moving.

References

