 - 2nd set – is applied between the upper and lower SwissTom arrays adopting the same positioning technique as set one with respect to the mid-axillary line. In patients with the 2nd SwissTom array on the thigh, the 2nd ScioSpec EIS is also applied in this same truncal location.
 - 3rd set – applied on the right upper arm, “+” leads on the outside of the arm and “-“ leads on the inside, sandwiching the bicep.
- Please see device descriptions on pg. 12 for further detail

System Setup

CLINICAL MONITOR		
1. Clinical monitor: Open the desktop icon “iCollect - shortcut”	 iCollect - Shortcut	

2. At the following menu, ensure the settings in the orange box are as shown below and click “Online”

Patient Case Methods

- Research team member will turn on device and enter study identifier data.
- Research team member applies the device sensors as per Appendix II
- Research team member will confirm that data is being acquired.
- Device will remain attached to each patient until any of the following:
 - Stable for 6 hours (no signs of hemodynamic deterioration)
 - Disposition via discharge from the ED or admission to a care unit
 - Development of change from baseline hypotension or tachycardia below or above limits respectively.
 - The patient wishes for the device to be removed.
- The following data will be collected from the sensors: heart rate and electrical activity via electrocardiogram, transcutaneous oxygen saturation, blood pressure and arterial waveforms via finger plethysmography. Lastly, sensor data will collect changing perfusion physiology via electrical impedance tomography system.
- The study coordinator will extract relevant data from the patient's chart to complete a case enrollment form.
 - Data points from chart-
 - Gender

- Age (by decade)
- Height
- Weight
- Medications given during the ED visit and admission (if patient is admitted)
- Vital signs at triage and at “change in status.”
- Based on clinical chart review, the PI and co-PI will independently adjudicate each patient into either the “likely ongoing hemorrhage” or “likely no ongoing hemorrhage” outcome categories without reference to the algorithm results. In the event of differing results, the PI and the co-PI will meet and discuss until consensus is reached.
- At the quarterly milestones the existing data will be used iteratively to refine the Phase II algorithm, creating an initial Phase III algorithm.

Data Acquisition and Storage:

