Uploaded de-identified data is stored in a secure server room at the Thayer School of Engineering and backed up nightly to a secure offsite facility operated by Dartmouth College. Access is limited to authorized users, based on the security model of the share. Access to data is via SMB or kerberized NFS protocols and allowed only from on-campus locations or over VPN. For any data shares that store Level 3 data (according to Dartmouth DISC policy), access is only allowed via VPN or from properly secured on-campus systems to ensure two-factor security.

Potential Risks:

The adhesives used on the electrodes can cause skin irritation. This risk should not be greater than that caused by our hospital ECG monitor. Tomography (EIT) and Near Infrared Spectroscopy (NIRS) may carry a risk of electrical sensation/shock or light exposure to eyes if the equipment malfunctions or gets displaced. There may be additional risks in this study which are not yet known.

Benefits:

None beyond participation in biomedical research.

Inclusion of Women and Minorities:

These groups will not be excluded from screening or enrollment in this convenience sample.

Inclusion of Children:

Children less than 18 years of age are excluded.

Inclusion of Adults with Impaired Decision-making Capacity: Adults with impaired decision-making capacity will not be included in this study.

Safety monitoring:

As this is a minimal risk, non-invasive study, we do not anticipate major changes in risks and benefits. Continual and prompt monitoring by the Principal Investigator of any unanticipated problems will be reported to the IRB and the sponsor.

No Significant Risk

All modules within the prototype are designed to conform to the International Electrotechnical Commission (IEC) 60601-1 safety standard for medical devices. Specifically, all devices are below the safety limits defined for Patient Auxiliary Currents which specifies that the maximum injected current for a diagnostic device is:

1. < 100 uA for frequencies < 1 kHz
2. < 100uA between 1 kHz and 100 kHz
3. < 10 mA for frequencies > 100 kHz

All devices are operated so the patient is floating with respect to the circuitry of the devices; ensuring that the patient is not exposed to appreciable DC current levels.

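### Protocol and Appendix II give opposite orders for power-on and sensor application, and in the Appendix II order internal fault-finding can take place with the patient attached

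*Combined protocol and SAP*

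**What the plan says.** **Protocol, Patient Case Methods.** The first bullet reads "Research team member will turn on device and enter study identifier data". The second has the sensors applied in the manner set out in Appendix II. The section then lists when monitoring ends: "Device will remain attached to each patient until any of the following", followed by four events. These are six hours of stability, "Disposition via discharge from the ED or admission to a care unit", hypotension or tachycardia beyond limits, and the patient's wish.

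**Protocol, Potential Risks.** EIT and NIRS "may carry a risk of electrical sensation/shock or light exposure to eyes if the equipment malfunctions or gets displaced".

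**Appendix II, Patient preparation.** The unit is plugged in at step 3. Step 5 is "Apply Electrical Impedance Tomography (EIT) electrodes – two (2) sets of 16 electrodes each", and steps 6 to 8 add the EIS electrodes, the NIRS probes and the clinical-monitor electrodes with the finger probe. System Configuration and Setup, where the system is turned on, comes next, and Initialize software packages follows.

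**Appendix II, fault steps.**
- EIS (Initialize software packages, step 4b): if port COM5 is not found and restarting first the software and then the computer does not help, "check the connections on the ISX-3 mini – requiring removal of the REAR panel of the enclosure". Staff then check the USB cable, unplug and replug the module's power cable, and cycle the module's switch.
- EIT (step 5a): if the Sensor Belt Connector shows as disconnected, "it indicates an internal power or connectivity problem, requiring the enclosure to be opened". Two connections are then checked.
- NIRS (Data Collection, step 4a): if one panel light stays on, power is cycled by switching off the uninterruptible power supply (UPS).

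**The concern.** The two sequences cannot both be followed. Which one staff use decides when an internal fault comes to light: before anyone is connected, or after the sensors are on an injured patient. In the second case the manual leads straight into opening the enclosure or cycling power, and says nothing about the patient at the other end of the leads.

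The protocol itself names malfunction as the circumstance in which EIT and NIRS could cause an electrical sensation, a shock or light exposure to the eyes. The statements of minimal risk and of a floating patient are made for the devices as operated. No section says whether they also cover work with a panel off. What is at stake is participant safety and the support for the no-significant-risk description. The sample size of 480 and the performance measures are not affected.

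**Working it through.** The point turns on the order of steps, so no arithmetic applies. The sequences side by side:

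| Stage | Patient Case Methods | Appendix II |
|---|---|---|
| First | Device on, study identifier entered | EIT, EIS, NIRS and monitor sensors applied (Patient preparation, steps 5–8) |
| Second | Sensors applied | System on (System Configuration and Setup) |
| Third | Data acquisition confirmed | COM5 and Sensor Belt checks (Initialize software packages, steps 4b and 5a) |
| Fourth | – | Check that all cables are attached, then recording (Data Collection) |

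**1. Is the patient attached when a start-up fault is found?** In the Appendix II order the sensors are on the skin. Whether the leads are also connected is an inference. Three things suggest that they are, at least in part. Staff are told that pads may be snapped to their fittings before they go on the patient (offered for comfort, not required). The clinical monitor is expected to show ECG and plethysmography data as soon as it starts. No later step applies sensors. Against this, the check that every cable is attached comes only at the head of Data Collection, after both start-up checks. Partial cabling is therefore probable, and full cabling is not established.

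**2. What happens at each fault?**

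| Fault | Enclosure opened | Power cycled | Patient leads addressed |
|---|---|---|---|
| EIS, step 4b, after both restarts fail | Yes, rear panel | Yes, ISX-3 mini module only | No |
| EIT, step 5a | Yes | No, two connections checked | No |
| NIRS, Data Collection step 4a | No | Yes, through the UPS | No |

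Two of the three fault steps open the enclosure and two cycle power. None tells staff to disconnect the patient. The only instruction to disconnect everything from the patient is Shutdown step 5, after the system is off. The NIRS step needs the least inference, because it follows the check that all cables are attached.

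**3. Does another section cover a malfunction?** None of the four removal events is an equipment fault. General Approach to Minimize Risk allows removal at any time. Study Design lets staff use fewer sensors for comfort or clinical circumstances. Neither is tied to a fault, but neither prevents removal for one.

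**4. Can the size be given?** No. The documents give no rate for a missing port, a disconnected belt connector or a NIRS panel error.

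**The case against.** The case on the other side has real force.

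- **Existing safeguards.** The protocol describes grounded components, a medical-grade UPS, current limits under IEC 60601-1 and a patient who floats relative to the circuitry. These stand, and they lower the likely severity. No text says that they hold with the enclosure open, and none says that they do not.
- **The steps are conditional.** They apply only to a fault and, for EIS, only after two restarts. This stands.
- **Scope of the cross-reference.** Patient Case Methods may cite Appendix II only for how sensors are applied, which would leave its own power-on-first order in force. That is a fair reading, but the manual still prints the reverse order and staff hold both texts.
- **Missing figures.** The figures in Appendix II could not be read in the text available here. A warning printed on one of them would answer part of the point.

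A reader might also infer more than the documents support:

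- *That the device may not be removed on a malfunction.* Removal at any time is expressly allowed. What is absent is a stated link to a fault, and that alone would only be missing detail.
- *That staff re-power the whole enclosure with the panel off.* In step 4b only one module is cycled. Step 5a involves no unplugging and no switch. The UPS step opens no panel.
- *That the manual keeps the patient attached in exactly the state said to cause shock.* Potential Risks names EIT and NIRS there, not EIS, and does not equate a missing port or loose connector with the malfunction it has in mind.
- *That every patient is fully wired at the check, or that a number exposed can be worked out.* Cabling at that point is inferred, fewer sensors are allowed, and any assumed rate of missing ports would overstate panel removals, since both restarts must fail first.

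**Conclusion.** The conflict in order is plain on the text. Followed as written, Appendix II permits internal fault-finding, or cycling of system power, with a patient attached, and no visible step addresses that patient. For the two start-up checks this rests on the inference that leads are at least partly connected. For the NIRS step it rests only on the earlier all-cables check having been done.

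The likely severity is limited by the electrical design, the frequency is unknown, and no patient count can be given. The point concerns device safety and operations and has no bearing on endpoints, power or analysis. It is worth acting on because the remedy is specific and close to free.

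**What to change.** 1. **Reconcile the order.** Bring Patient Case Methods and Appendix II into line so that power-on and the COM5 and Sensor Belt checks are done before patient leads are connected, as the order in Patient Case Methods already implies. The manual traces both faults to the device or its internal connections, so the checks should not need a patient. The sponsor can confirm this on the bench.
2. **Amend the three fault steps.** In steps 4b and 5a and in the NIRS power step, state that patient leads are disconnected from the system before a panel is opened or system power is cycled. Do not require the system to be unplugged throughout: step 4b relies on the computer sounding when it recognises the USB connection, which needs power.
3. **Reconcile the removal list with the risk text.** The removal events in Patient Case Methods and the malfunction risk in Potential Risks should be made consistent. The rule is for the sponsor to decide, and none is proposed here.

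The cost is a reordered manual and a few sentences. The downside is a few minutes of reconnection, and a possible gap in recording, in sessions with a fault.
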